11.7 Interim Analysis

An interim analysis is not planned for this study.

12 ADMINISTRATIVE CONSIDERATIONS

12.1 Institutional Review Board or Research Ethics Board Approval

The responsible Institutional Review Board (IRB) or Research Ethics Board (REB) must be constituted according to the applicable local and national requirements of each participating location. The Sponsor or its designee will require documentation noting all names and titles of members who compose the respective IRB/REB. If any member of the IRB/REB has direct participation in this trial, written notification regarding his or her abstinence from voting must also be obtained.

The Sponsor or its designee will supply relevant documents for PIs to submit to their respective IRB/REB for the review and approval of the protocol. The Investigator will not enroll subjects into the study until the Investigator has received written approval for, or written favorable opinion on, the protocol, the informed consent document(s), and any planned recruitment aids from their IRB/REB. The IRB/REB approval must: refer to the study by the exact protocol title, number, and version date; identify versions of other documents (e.g., subject or care partner ICFs) reviewed; and state the approval date. The Investigator will make all required progress reports to their IRB/REB in writing in a timely manner and will obtain all required approvals in writing (at least annually in all cases) to continue to participate in the study.

The Investigator will promptly report to their IRB/REB any unanticipated problems associated with the study devices involving risks to subjects or others, whether encountered at their site or provided as a safety report by the Sponsor/designee.

Sites must adhere to all requirements stipulated by their respective IRB/REB. The Investigator will promptly notify their IRB/REB of any planned protocol amendment and will not implement any protocol amendment until the IRB/REB has provided written approval of, or written favorable opinion on, the amendment.

12.2 Ethical Conduct of the Study

This study will be conducted in accordance with the ethical principles that have their origin in the Declaration of Helsinki (Edinburgh 2000), the ethical and quality standards of good clinical practice (ICH E6) and all applicable regulatory requirements and laws.²⁰

The PI will provide all necessary information on the protocol and the study device to all physicians, nurses, and other personnel who participate in this study under the PI's supervision and will discuss this material with them as needed, to ensure that they are fully informed regarding the conduct of the study and the potential effects of the study device.

12.3 Compliance with Protocol and Protocol Amendments

The Investigator, and all physicians, nurses, and other personnel who participate in this study under the Investigator's supervision, will conduct the study according to the currently approved version of the protocol. In cases where the protocol is not followed, the site staff will document the reason for the deviation from the protocol and any corrective actions taken and/or preventative measures put in place to avoid future occurrences. Serious or repeated deviations from the protocol will result in termination of the Investigator's participation in the study.

Neither the Investigator, nor the sponsor, will amend or modify the protocol without notifying the other. Any protocol amendment must be: approved by DEKA R&D Corp. and CVS Pharmacy Inc., a CVS Health Company, in writing; agreed to by the Investigator in writing; and approved by the Investigator's IRB/REB in writing prior to implementation of the amendment.

12.4 Subject Information and Consent

The nature of the study will be fully explained to each potential subject and care partner and voluntary, written (signed and dated) informed consent will be obtained from the subject and care partner prior to enrolling the subject in the study. No study-specific procedures will be performed prior to the Investigator or their designee obtaining written informed consent.

Preparation of the ICF is the responsibility of the PI and must include all elements required by GCP and applicable regulatory requirements and must adhere to GCPs and to the ethical principles that have their origin in the Declaration of Helsinki (see Appendix 5 for the requirements of an informed consent statement). All ICFs must be reviewed by the Sponsor prior to IRB/REB submission. Only subjects with the initial intention to complete the study should be considered for entry into the study.

The PI must provide the subject/care partner or a legal representative with a copy of each ICF and written information about the study in English only. The language must be nontechnical and easily understood. The PI should allow the time necessary for the subject or the subject's legal representative to inquire about the details of the study after which the ICF must be signed and personally dated by the subject or by the subject's legally acceptable representative and by the person who conducted the informed consent discussion. The subject or a legal representative should receive a copy of the signed ICF, and any other written information provided to the study subject prior to the subject's participation in the trial. The PI must furnish the Sponsor or its designee with a copy of each IRB/REB-approved ICF to be used in this study prior to the commencement of the study.

12.5 Subject Confidentiality

All subject information, medical records, and laboratory data will be kept confidential.

Information and data may be discussed, analyzed, and reported; however, code numbers will identify the subject on the eCRFs and in any reports, and the subject's identity will be kept confidential.

12.6 Protocol Violations/Deviations

Protocol violations/deviations will be documented in source for transmission into a tracking system. The clinical team will review deviations at a study level on a regular basis for issues and resolution.

12.7 Access to Source Documentation

Monitoring visits will occur at regularly scheduled intervals at the investigational site to allow for verification of source documents and comparison of source data with the information recorded on the eCRFs.

Representatives of the Sponsor, or its designee, must be allowed to visit the study site regularly to assess the data quality and the integrity of the study. These representatives will review study records on site and directly compare these with the source documents, discuss the conduct of the study with the PI, and verify that the facilities remain acceptable. In addition, the study may be evaluated by the Sponsor's internal auditors or a designee, and/or by government inspectors, who must be allowed access to eCRFs, source documents, and other study files.

The PI or a designated member of the PI's staff must be available at some time during monitoring visits to review data and resolve any queries and to allow direct access to the subject's records (e.g., medical records, office charts, hospital charts, and study-related charts) for source data verification. The eCRFs should be completed prior to each visit and be made available to the monitor so that their accuracy and completeness may be checked.

If an onsite visit is not possible due to public health or patient safety concerns, the site must provide electronic copies of source documentation to enable a remote monitoring visit, to ensure continued review of data quality and integrity of the study. The Sponsor or designee will work with the site to enable this according to all federal, local, and institutional Patient Health Information protective measures.

This study may be subject to an independent audit at the investigational site, which will be conducted by independent auditors. Full consultation with appropriate personnel will be made prior to and during such audit. The PI must be available during the audit. If the PI is contacted by any regulatory authority regarding an audit for this study or any other study, the PI will contact the Sponsor/designee immediately.

12.8 Retention of Data

The PI must retain all study records including IP disposition records, and source documents (including informed consent documents, safety reports, etc.) for the maximum period required by applicable regulations and guidelines or institution procedures or for the period specified by Sponsor/designee, whichever is longer. The PI must contact the Sponsor before destroying any records associated with the study. The Sponsor or its designee will notify the PI when the trial records are no longer needed. If the PI withdraws from the study (e.g., relocation, retirement), the records shall be transferred to a mutually agreed upon designee (e.g., another PI, IRB). The Sponsor/designee will be notified in writing of any such transfer.

12.9 Publication and Disclosure Policy

Any information shared by the Sponsor regarding this study, including this protocol, is

considered proprietary information and should be kept confidential.

The data generated by this clinical study are the property of the Sponsor. These data may be used by the Sponsor, now and in the future, for presentation or publication at the Sponsor's discretion or for submission to regulatory agencies. In addition, the Sponsor reserves the right of prior review of data from this study relative to the potential release of proprietary information to any publication or for any presentation.

Appendix 1 Schedule of Evaluations and Procedures

Schedule of Evaluations and Procedures

Observation	Qualification Visit	Each Visit During Treatment Period	End of Study Visit
Informed Consent of subject and care partner	X		
Medical History Update ¹	X		
Physical examination	8		X
Vital signs		X	
Weekly Assessment by the investigator or designee		X	
Clinical observations ²		X	X
AE/SAE/ADE ³	X	X	X
Concomitant medications update ⁴	X	X	X
Clinical laboratory evaluations ⁵		X	X
Machine observations ⁶		X	
Ultrapure sampling ⁷		X	
Visual assessment of the HemoCare™ Blood Treatment Set ⁸		X	
Device-related product issues (Device-related complaints)9		X	X
Chloramine, pH, and conductivity testing ¹⁰		X	

- Adverse events that have resolved as of DKPL-00057-001 end of study visit will be included as medical history.
- Clinical observations will occur per treatment.
- Ongoing AEs and SAEs will be included from DKPL-00057-001 and any new AEs and SAEs will be collected after the informed consent is signed. ADEs will be collected from the first connections of the subject to the HemoCareTM Hemodialysis System.
- 4. Ongoing medications and any new medications taken will be recorded throughout the study.
- 5. Clinical laboratory evaluations are presented in detail in Appendix 2.
- Ultrapure samples will be collected at least quarterly or according site policy or to local regulations after subject rolls over from Protocol DKPL-00057-001.
- Visual assessment of the HemoCare™ Blood Treatment Set will occur before every treatment on the HemoCare™ Hemodialysis System.
- Collection of device-related product issues (device-related complaints) will begin at the time the HemoCareTM Hemodialysis System is installed at the investigational site and assigned to a subject and this will continue throughout the entire study.
- Chloramine, pH, and conductivity testing will occur before every treatment on the HemoCare™ Hemodialysis System according to standard-of-care and local requirements.

11

6.

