8 ADVERSE EVENT REPORTING

8.1 Adverse Events and Serious Adverse Events

An AE is any untoward medical occurrence in a subject administered a study product and which does not necessarily have a causal relationship with the treatment or study product.

An AE can therefore be any unfavorable and unintended sign (including an abnormal laboratory function), symptom (e.g., rash, pain, discomfort, fever, dizziness, etc.), disease (e.g., bacteremia, pancreatitis, etc.) or outcome of death temporally associated with the use of the study product, whether or not the event is considered to have a causal relationship with the study product.

Laboratory and vital sign abnormalities qualify as AEs if medical intervention is required to treat or address the abnormality, if the subject must be discontinued from the study due to the abnormality, or if the value exceeds specific limits defined by the protocol as qualifying it as an AE (see Appendix 4).

An elective procedure/surgery that occurs during the course of a study but is being performed for a documented pre-existing condition and was pre-planned prior to study entry will not qualify as an AE. If, however, the pre-existing condition unexpectedly deteriorates during the study requiring the procedure/surgery to be performed earlier than planned, the condition for which the procedure/surgery is being performed will qualify as an AE.

Adverse events will be collected starting from the time the subject signs the ICF until the end of the study. If an AE occurs, a full description of the event should be recorded including the date of onset, severity, time course, description, actions taken, and causal relationship of the AE to the study product(s). Investigators should review and reference the Causality definitions below when determining relationship of the AE to the study product. The Investigators may also discuss the event(s) with the Medical Monitor, but the Investigator must make, document and report the relationship for every AE. All AEs must be documented in source documents and on the eCRFs, no matter how common they are for a particular subject and regardless of the causality assigned by the Investigator.

All AEs and SAEs, regardless of relatedness, should be actively solicited and recorded.

Additionally, any AE voluntarily reported by the subject should be recorded and verified by the Investigator or designee on the appropriate source documents and eCRF pages.

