8.1.9 Performing Adverse Events Assessments

The AE collection period for each subject starts with the signing of the ICF and completes when the subject ends the study. During the course of the study, the Investigator or designee shall routinely monitor each subject for the occurrence of any AE. Routine monitoring should include regular communication with the trial subject, review of laboratory results, assessment of anticoagulation, dialysis access, medication use, and review of the treatment details in the HemoCareTM cloud-based system as reported by the assigned HemoCareTM Hemodialysis System. Site team members should follow up and gather additional details from subjects when appropriate based on these information sources as well other data sources including but not limited to physical exams, vital signs, subject questionnaires, and concomitant medication listings.

In addition to AE solicitation, study sites should discuss the AE reporting process with their study subjects and encourage them to volunteer the applicable information to the appropriate site team members in real time. All site team members should likewise monitor and solicit information from subjects if an event is suspected based on subject conversations or data points collected. This level of open dialog should drive the AE collection and reporting process.

During the course of the study, controls will also be in place to consistently gather AE information during the Weekly Assessment. The site team members will use their clinical judgment to follow up with the subjects and report any applicable event(s).

The site investigator or designee will contact the subject weekly to discuss their current status, treatment, and condition. These timelines are minimum requirements

for the sites to follow, and sites should follow their local guidelines if more frequent communication is required (e.g., local standard of care or to follow up on current/recent events).

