9.2 Qualification Visit

The Qualification visit will be conducted after completion of DEKA Protocol DKPL-00057-001. The study must be explained to the subjects and care partners at this visit or prior, and all subjects and care partners must sign an ICF before any study-related procedures are performed. The following procedures will be performed and, as appropriate, recorded on the eCRF at the Qualification visit:

- Obtain informed consent of the subject and care partner.
- · Update medical history including resolved AEs.
- Update concomitant medications.
- Update AEs including ongoing AEs.

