11.3 Analysis Populations

The Intent-to-Treat (ITT) population will include all subjects who have used the HemoCare™ Hemodialysis System at least once in this rollover study. All analyses will be performed on the ITT population unless otherwise noted.

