11.5 Primary Endpoints

11.5.1 Primary Safety Endpoint(s)

Safety endpoints will summarize the number of subjects having AE and the number of AE: Number and proportion of subjects having AE and SAE, Number of AE and SAE, and rate of AE/100-Treatment and SAE/100-Treatment.

All the above indicator will be broken down by SOC, PT, Anticipated/unanticipated, and Related/un-related.

Safety will be assessed by evaluating AEs. In addition, monthly laboratory draws will be assessed.

Adverse events will be mapped to a primary MedDRA SOC and PT. Anticipated AEs and SAEs (includes all AEs related to dialysis as identified in Section 8.1.7) and unanticipated AEs and SAEs (excludes all AEs related to dialysis identified in Section 8.1.7) will be summarized during by SOC and PT. In addition, all device-related AEs and SAEs will be summarized by SOC and PT.

An overview of the total number of AEs and SAEs (anticipated, unanticipated, and device- related) will be provided. In addition, an overview will be provided of the total number of subjects having at least one:

[figure not shown]
- a. anticipated AE
- b. anticipated SAE
- c. unanticipated AE
- d. unanticipated SAE
- e. device-related AE
- f. device-related SAE (UADE)

The proportion of subjects having at least one AE within each of these six AE subgroups will be summarized descriptively.

Furthermore, the proportion of subjects having AEs within each of these six AE subgroups will be summarized by SOC, PT and severity (mild, moderate or severe) for the most severe rating of each AE per subject. And, the AE rate per 100 HemoCareTM Hemodialysis System treatments will be calculated.

Descriptive summary statistics will be provided for the visit values and change from DEKA Protocol DKPL-00057-001 baseline in monthly laboratory draws.

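### AEs still ongoing from the parent study are carried into this study's AE data, and section 11.5.1 counts AEs with no onset or worsening condition, so events that began before rollover can enter the primary safety figures

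*Combined protocol and SAP*

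**What the plan says.** **What enters the AE data.** Appendix 1 splits parent-study events in two. For resolved events: "Adverse events that have resolved as of DKPL-00057-001 end of study visit will be included as medical history". For the others, the footnote to the AE/SAE/ADE row says: "Ongoing AEs and SAEs will be included from DKPL-00057-001 and any new AEs and SAEs will be collected after the informed consent is signed". Section 9.2 makes the same split: resolved events update the medical history, while the AE step reads "Update AEs including ongoing AEs".

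**When collection starts.** Section 8.1: "Adverse events will be collected starting from the time the subject signs the ICF until the end of the study". Section 8.1.9 agrees: "The AE collection period for each subject starts with the signing of the ICF and completes when the subject ends the study". Neither mentions events that began earlier. For adverse device effects, the Appendix 1 footnote starts collection at the subject's first connection to the system, without saying in which study.

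**What is counted.** Section 11.5.1 lists "Number and proportion of subjects having AE and SAE, Number of AE and SAE, and rate of AE/100-Treatment and SAE/100-Treatment", broken down by SOC, PT, anticipated or unanticipated, and related or unrelated. It adds that "the AE rate per 100 HemoCareTM Hemodialysis System treatments will be calculated". The synopsis has the same subgroup summaries and rate. The analysis population in section 11.3 is "all subjects who have used the HemoCare™ Hemodialysis System at least once in this rollover study", which selects subjects, not events.

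**What is recorded.** The AE eCRF (section 8.1.10.1) holds start and stop dates, one severity item, and a timing item with a category for events before the first study treatment. No analysis rule in the supplied text uses the start date or that category.

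**The concern.** The objective in section 3 is the safety of continued access. A reader will take the AE table as what happened after rollover. If carried-over events are counted, part of it describes the parent study instead.

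The rates have a further problem. An event that arose under parent-study treatment would stand in the numerator, while the treatments during which it arose would be missing from the denominator. Section 11.5.1 does not define the denominator period, but rollover treatments are the natural reading.

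Two programmers could follow the protocol faithfully and produce different primary tables. Thin cells are the most exposed, such as unanticipated SAE or device-related SAE. There, a single event decides whether the line is empty.

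**Working it through.** The plan states no AE rate, rollover sample size or number of events ongoing at rollover, so there is no figure to reproduce. The check has two parts.

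**1. Does any visible rule keep a pre-rollover event out of the counts?** Take an AE that began in the parent study and is unresolved at its end-of-study visit.

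- Medical history (Appendix 1, 9.2): takes resolved events only, so this one stays in the AE data.
- Sections 8.1 and 8.1.9: set when collection starts, not what is analysed.
- Section 11.3: keeps the event if the subject has one rollover treatment.
- Section 11.5.1 and synopsis: no onset, worsening or treatment-emergence condition.

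Nothing in the supplied text removes it.

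**2. How large could the effect be?** Assumptions: N = 30, from the approximate number the parent study aims to bring into its unassisted period (section 2.1); 3 to 6 treatments per week, the range given in section 2.1 for extended therapies; and several follow-up times, because section 4.3 leaves duration open. The numbers of events are also assumed.

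*Thin categories.* Each subject carrying in an event, with no new event in that category, adds 1/N. At N = 30, 1/30 = 3.3 percentage points, so 0/30 becomes 1/30. The parent's enrolment cap of 70 gives 1/70 = 1.4 points. That is a floor rather than a realistic value, since only completers roll over.

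*Relative overstatement.* With k carried-over and m new events over the same denominator, counts and rates are overstated by k/m. For k = 1:

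| New events m | Overstatement |
|---|---|
| 2 | 50% |
| 5 | 20% |
| 20 | 5% |
| 50 | 2% |

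Since k is fixed at rollover and m grows with follow-up, the ratio falls over time.

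*Absolute rate.* One event adds 100 / (N × treatments per week × weeks), with 52 weeks per year:

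| Follow-up | Treatments (3 to 6 per week) | Added per 100 treatments |
|---|---|---|
| 1 month | 390 to 780 | 0.256 to 0.128 |
| 6 months | 2,340 to 4,680 | 0.043 to 0.021 |
| 1 year | 4,680 to 9,360 | 0.021 to 0.011 |
| 2 years | 9,360 to 18,720 | 0.011 to 0.005 |

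If 10% to 30% of the 30 subjects each carried in one event (3 to 9 events), the one-year addition would be 0.03 to 0.19 per 100 treatments.

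*Proportion with any AE.* If a share p has a new AE and a share c independently carries one in, the reported proportion is 1 − (1 − p)(1 − c). For c = 10%, 20% and 30%:

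- p = 30% becomes 37%, 44% and 51%.
- p = 50% becomes 55%, 60% and 65%.
- p = 80% becomes 82%, 84% and 86%.

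The gap narrows as p rises with longer follow-up.

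**The case against.** **Inclusion may mean follow-up only.** Section 8.1 requires device-related AEs and all SAEs to be followed until resolved or stable, and carrying open events forward serves that. This is a fair reading, and it is why the point is that such events *can* enter the counts, not that they will. It does not settle the matter, because 11.5.1 does not limit inclusion to follow-up.

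**The rule may be elsewhere.** Section 11.1 leaves analysis conventions to a SAP, and the supplied numbering runs from 11.5.1 to 11.7. A treatment-emergent rule could sit in either place. This stands: a reader might infer that no such rule exists, but the supplied text cannot show that. What it does show is a stated inclusion step with no matching limit in the endpoint section.

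**A contradiction between sections is not there.** A reader might infer that Appendix 1 conflicts with 8.1 and 8.1.9. It does not. All three start new events at consent; Appendix 1 adds older ones for which 8.1 and 8.1.9 have no wording.

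**The thin-category case is speculative.** It needs an unresolved event of that kind in a subject whom the investigator still judges qualified, with stable vascular access and no interfering condition (5.2, 5.3). Nothing suggests that this is common. The objection bears on likelihood, not on what happens if it occurs.

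**An onset-only rule could hide harm.** This stands. A mild parent-study event that becomes severe or serious during rollover would drop out of the primary counts. The remedy must therefore cover worsening.

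**Conclusion.** The point holds as a gap in the counting rule: on the supplied text, events that began before rollover can be counted as safety events of continued access. It is a cheap improvement, minor to should-fix.

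The error would overstate harm. A reader might infer that the overall AE rate would be seriously distorted. The documents do not support that: they give no number of ongoing events, and at N = 30 one event moves the rate by about 0.01 to 0.02 per 100 treatments over an assumed year. The visible risk is in thin categories, where one such event turns 0% into 3.3%. Nor do the documents support inferring that an event would be counted twice across the two studies, since they describe no pooled analysis. The study is descriptive, with no power calculation and no planned interim analysis, so no test or error rate is affected. The monthly laboratory summaries are untouched.

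All sizes rest on the assumed N, treatment frequency, follow-up and event numbers.

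**What to change.** In section 11.5.1, the synopsis and the SAP, unless the SAP already has such a rule:

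- **(a)** Count in the primary AE and SAE numbers, proportions and rates only events with onset, or with worsening in severity or seriousness, on or after signature of the rollover consent form.
- **(b)** List all other events carried over from DKPL-00057-001 in a separate table.
- **(c)** Define the per-100-treatment denominator as HemoCare treatments given in this rollover study.

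In data collection and Appendix 1:

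- **(d)** Have post-consent worsening of a carried-over event entered as a new AE record with its own start date. The listed eCRF items include start and stop dates and a single severity grade but no date of worsening, so without this step the worsening part of (a) cannot be applied.
- **(e)** State in the footnote that carried-over events are included for follow-up, and which study's first connection starts ADE collection.

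Cost: a few sentences, one footnote edit, one derived flag and a small eCRF instruction. Start dates are already collected, so the onset part needs no new data. The downside is slightly fewer AEs in the headline counts; the carried-over events stay visible in their own table.
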